7.1. Discontinuation of Study Intervention

When necessary, a participant may be permanently discontinued from study intervention. If so, the participant will remain in the study to complete procedures for an ED visit and post-treatment follow-up, if applicable, as shown in the SoA.

A participant should be permanently discontinued from study intervention if

- the participant becomes pregnant during the study
- in the opinion of the investigator, the participant should permanently discontinue the study intervention for safety reasons
- if the investigator determines that a systemic hypersensitivity reaction has occurred related to study intervention administration, the participant may be permanently discontinued from the study intervention, and the sponsor's designated medical monitor should be notified. If the investigator is uncertain about whether a systemic hypersensitivity reaction has occurred and whether discontinuation of study intervention is warranted, the investigator may consult the sponsor
- the participant has an AE or an SAE or a clinically significant change in a laboratory value that, in the opinion of the investigator, merits discontinuation of study intervention and appropriate measures being taken
- if the participant experiences a hepatic event or liver test abnormality as specified in the liver chemistry stopping criteria (see Section 7.1.1), and
- HBV or HCV: The participant tests positive for HBV DNA (see Section 8.2.5) or tests positive for HCV RNA (Section 8.2.6).

Note: The HBV DNA result is to be confirmed if initial positive test result is positive but below the level of quantification. Prior to discontinuation of any immunomodulatory and/or immunosuppressive therapy, including study intervention, the participant is to be referred to, evaluated, and managed by a specialist physician with expertise in evaluation and management of viral hepatitis. The timing of discontinuation from study intervention relative to the initiation of any antiviral treatment for hepatitis is to be based on the recommendation of the consulting specialist physician, in conjunction with the investigator, and aligned with medical guidelines and standard of care.

7.1.1. Liver Chemistry Stopping Criteria

The study drug should be interrupted or discontinued if 1 or more of these conditions occur:

Elevation	Exception
ALT or AST >8x ULN	
ALT or AST >5x ULN for more than 2 weeks	
ALT or AST >3x ULN and either TBL >2x ULN or INR >1.5	In participants with Gilbert's syndrome, doubling of direct bilirubin should be used for drug interruption/ discontinuation decisions rather than TBL >2x ULN
ALT or AST >3x ULN with the appearance of fatigue, nausea, vomiting, right upper quadrant pain or tenderness, fever, rash, and/or eosinophilia (>5%)	
ALP >3x ULN, when the source of increased ALP is the liver	
ALP >2.5x ULN and TBL > 2x ULN	In participants with Gilbert's syndrome, doubling of direct bilirubin should be used for drug interruption/ discontinuation decisions rather than TBL>2x ULN
ALP >2.5x ULN with the appearance of fatigue, nausea, vomiting, right upper quadrant pain or tenderness, fever, rash, and/or eosinophilia (>5%)	

Source: FDA Guidance for Industry: Drug-Induced Liver Injury: Premarketing Clinical Evaluation, July 2009 and other consensus guidelines, with minor modifications

Abbreviations: ALP = alkaline phosphatase; ALT = alanine aminotransferase; AST = aspartate aminotransferase; INR = international normalized ratio; TBL = total bilirubin; ULN= upper limit of normal.

Resumption of the study drug can be considered only in consultation with the Lilly-designated medical monitor and only if the liver test results return to baseline and if a self-limited, non-drug etiology is identified.

7.1.2. QTc Stopping Criteria

If a clinically significant finding is identified, including, but not limited to changes from baseline in QT interval corrected using Fridericia's formula (QTcF) after enrollment, the investigator or qualified designee will determine if the participant can continue in the study and if any change in participant management is needed. This review of the ECG printed at the time of collection must be documented. Any new clinically relevant finding should be reported as an AE.

7.1.3. Temporary Discontinuation

If for some reason, study intervention is temporarily stopped for reasons other than safety, participant should resume intervention as soon as possible.

7.1.4. Rechallenge

If study intervention is temporarily stopped for safety, participants may be rechallenged with study intervention once if appropriate in the opinion of the investigator.

7.2. Participant Discontinuation/Withdrawal from the Study

Discontinuation is expected to be uncommon.

A participant may withdraw from the study:

- at any time at the participant's own request
- at the request of the participant's designee, for example, parents or legal guardian
- at the discretion of the investigator for safety, behavioral, compliance, or administrative reasons
- if enrolled in any other clinical study involving an investigational product, or enrolled in any other type of medical research judged not to be scientifically or medically compatible with this study

At the time of discontinuing from the study, if possible, the participant will complete procedures for an ED visit and post-treatment follow-up, if applicable, as shown in the SoA. If the participant has not already discontinued the study intervention, the participant will be permanently discontinued from the study intervention at the time of the decision to discontinue the study.

If the participant withdraws consent for disclosure of future information, the sponsor may retain and continue to use any data collected before such a withdrawal of consent. If a participant withdraws from the study, the participant may request destruction of any samples taken and not tested, and the investigator must document this in the site study records.

7.3. Lost to Follow up

A participant will be considered lost to follow-up if he or she repeatedly fails to return for scheduled visits and is unable to be contacted by the study site. Site personnel or designee are expected to make diligent attempts to contact participants who fail to return for a scheduled visit or were otherwise unable to be followed up by the site.

Site personnel, or an independent third party, will attempt to collect the vital status of the participant within legal and ethical boundaries for all participants randomized, including those who did not get investigational product. Public sources may be searched for vital status information. If vital status is determined to be deceased, this will be documented and the participant will not be considered lost to follow-up. Sponsor personnel will not be involved in any attempts to collect vital status information.

8. Study Assessments and Procedures

- Study procedures and their timing are summarized in the SoA.
- Immediate safety concerns should be discussed with the sponsor immediately upon occurrence or awareness to determine if the participant should continue or discontinue study intervention.
- Adherence to the study design requirements, including those specified in the SoA, is essential and required for study conduct.
- All screening evaluations must be completed and reviewed to confirm that potential participants meet all eligibility criteria. The investigator will maintain a screening log to record details of all participants screened and to confirm eligibility or record reasons for screening failure, as applicable.

8.1. Efficacy Assessments

8.1.1. Primary Efficacy Assessment

Elevated Lp(a) is recognized as an important risk factor for cardiovascular disease. Lp(a) will be collected for each participant at the times shown in the SoA (Section 1.3).

8.1.2. Secondary Efficacy Assessments

The 2018 AHA/ACC Guideline on the management of blood cholesterol identified Lp(a) ≥50 mg/dL (≥125 nmol/L) as risk enhancing. As a responder analysis, the proportions of participants achieving Lp(a) <125 nmol/L at Week 12 will be assessed.

At times specified in the SoA, blood samples will be collected to measure changes in levels of these markers

- ApoB
- hsCRP

See Section 9.3 for definitions of the efficacy endpoints.

8.2. Safety Assessments

Planned time points for all safety assessments are provided in the SoA.

8.2.1. Electrocardiograms

Single 12-lead ECG will be obtained as outlined in the SoA (see Section 1.3) using an ECG machine that automatically calculates the heart rate and measures PR, QRS, QT, and QTc intervals. Refer to Section 7.1.2 for QTc withdrawal criteria and any additional QTc readings that may be necessary.

8.2.2. Clinical Safety Laboratory Tests

• See Appendix 10.2 for the list of clinical laboratory tests to be performed and the SoA for the timing and frequency.

• The investigator must review the laboratory results, document this review, and report any clinically relevant changes occurring during the study as an AE. The laboratory results must be retained with source documents unless a Source Document Agreement or comparable document cites an electronic location that accommodates the expected retention duration. Clinically significant abnormal laboratory findings are those which are not associated with the underlying disease, unless judged by the investigator to be more severe than expected for the participant's condition.

- All laboratory tests with values considered clinically significantly abnormal during participation in the study or within 4 weeks after the last dose of study intervention should be repeated until the values return to normal or baseline or are no longer considered clinically significant by the investigator or medical monitor.
 - If such values do not return to normal/baseline within a period of time judged reasonable by the investigator, the etiology should be identified and the sponsor notified.
 - All protocol-required laboratory assessments, as defined in Appendix 10.2, must be conducted in accordance with the SoA, standard collection requirements, and laboratory manual.
- If laboratory values from non-protocol-specified laboratory assessments performed at an investigator-designated local laboratory require a change in participant management or are considered clinically significant by the investigator, for example, SAE or AE or dose modification, then report the information as an AE.

8.2.3. Hepatic Safety Close hepatic monitoring

Laboratory tests (Appendix 10.6), including ALT, AST, ALP, TBL, direct bilirubin (D. Bil), gamma-glutamyltransferase (GGT), and creatine kinase (CK), should be repeated within 48 to 72 hours to confirm the abnormality and to determine if it is increasing or decreasing, if 1 or more of these conditions occur:

If a participant with baseline results of	develops the following elevations:
ALT or AST <1.5x ULN	ALT or AST ≥3x ULN
ALP <1.5x ULN	ALP ≥2x ULN
TBL <1.5x ULN	TBL ≥2x ULN, except for participants with Gilbert's syndrome
ALT or AST ≥1.5x ULN	ALT or AST ≥2x baseline
ALP ≥1.5x ULN	ALP ≥2x baseline
TBL ≥1.5x ULN	TBL ≥1.5x baseline, except for participants with Gilbert's syndrome

If the abnormality persists or worsens, clinical and laboratory monitoring, and evaluation for possible causes of abnormal liver tests should be initiated by the investigator in consultation with the Lilly-designated medical monitor. At a minimum, this evaluation should include physical examination and a thorough medical history, including symptoms, recent illnesses (for example, heart failure, systemic infection, hypotension, or seizures), recent travel, history of concomitant medications (including over the counter), herbal and dietary supplements, history of alcohol drinking and other substance abuse.

Initially, monitoring of symptoms and hepatic biochemical tests should be done at a frequency of 1 to 3 times weekly, based on the participant's clinical condition and hepatic biochemical tests. Subsequently, the frequency of monitoring may be lowered to once every 1 to 2 weeks, if the participant's clinical condition and laboratory results stabilize. Monitoring of ALT, AST, ALP, and TBL should continue until levels normalize or return to approximate baseline levels.

Comprehensive hepatic evaluation

A comprehensive evaluation should be performed to search for possible causes of liver injury if 1 or more of these conditions occur:

If a participant with baseline results of	develops the following elevations:
ALT or AST <1.5x ULN	ALT or AST ≥3x ULN with hepatic signs/symptoms ^a , or ALT or AST ≥5x ULN
ALP <1.5x ULN	ALP ≥3x ULN
TBL <1.5x ULN	TBL ≥2x ULN (except for participants with Gilbert's syndrome)
ALT or AST ≥1.5x ULN	ALT or AST $\ge 2x$ baseline with hepatic signs/symptoms ^a , or ALT or AST $\ge 3x$ baseline
ALP≥1.5x ULN	ALP ≥2x baseline
TBL≥1.5x ULN	TBL ≥2x baseline (except for participants with Gilbert's syndrome)

^a Hepatic signs or symptoms are severe fatigue, nausea, vomiting, right upper quadrant abdominal pain, fever, rash, and/or eosinophilia >5%.

At a minimum, this evaluation should include physical examination and a thorough medical history, as outlined above, as well as tests for prothrombin time (PT)-INR; tests for viral hepatitis A, B, C, or E; tests for autoimmune hepatitis; and an abdominal imaging study, for example, ultrasound or CT scan.

Based on the participant's history and initial results, further testing should be considered in consultation with the Lilly-designated medical monitor, including tests for hepatitis D virus (HDV), cytomegalovirus (CMV), Epstein-Barr virus (EBV), acetaminophen levels, acetaminophen protein adducts, urine toxicology screen, Wilson's disease, blood alcohol levels, urinary ethyl glucuronide, and blood phosphatidylethanol. Based on the circumstances and the investigator's assessment of the participant's clinical condition, the investigator should consider referring the participant for a hepatologist or gastroenterologist consultation, magnetic resonance cholangiopancreatography, endoscopic retrograde cholangiopancreatography, cardiac echocardiogram, or a liver biopsy.

Additional hepatic data collection (hepatic safety CRF) in study participants who have abnormal liver tests during the study

Additional hepatic safety data collection in hepatic safety CRF should be performed in study participants who meet 1 or more of the following 5 conditions:

- 1. Elevation of serum ALT to ≥5x ULN on 2 or more consecutive blood tests, if baseline ALT <1.5x ULN
 - ➤ In participants with baseline ALT \ge 1.5x ULN, the threshold is ALT \ge 3x baseline on 2 or more consecutive tests
- 2. Elevated TBL to \geq 2x ULN, if baseline TBL <1.5x ULN, except for cases of known Gilbert's syndrome
 - ➤ In participants with baseline TBL \ge 1.5x ULN, the threshold should be TBL \ge 2x baseline
- 3. Elevation of serum ALP to $\ge 2x$ ULN on 2 or more consecutive blood tests, if baseline ALP < 1.5x ULN
 - ➤ In participants with baseline ALP \ge 1.5x ULN, the threshold is ALP \ge 2x baseline on 2 or more consecutive blood tests
- 4. Hepatic event considered to be an SAE
- 5. Discontinuation of study drug due to a hepatic event

Note: the interval between the 2 consecutive blood tests should be at least 2 days.

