- 22. Lipoprotein apheresis within 3 months of Visit 1, or planned during the study.
- 23. Treatment with another investigational drug, biological agent, or device within 1 month of Visit 1, or 5 half-lives of investigational agent, whichever is longer.
- 24. Treatment with any investigational oligonucleotide or siRNA within 9 months of Visit 1.

Prior/Concurrent Clinical Study Experience

25. Are currently enrolled in any other clinical study involving an investigational product or any other type of medical research judged not to be scientifically or medically compatible with this study.

Diagnostic Assessments

- 26. Clinically significant abnormalities in screening laboratory values that would render a participant unsuitable for inclusion in the opinion of the investigator.
- 27. Any of the following abnormalities:
 - a. estimated glomerular filtration rate (eGFR) <30 mL/min/1.73 m²
 - b. alanine aminotransferase (ALT) or aspartate aminotransferase (AST) >3.0x upper limit of normal (ULN)
 - c. bilirubin > 1.5x ULN, except for participants diagnosed with Gilbert's syndrome

Other Exclusions

- 28. Are Lilly employees, or are employees of any third party involved in a study that requires exclusion of their employees.
- 29. Are investigator site personnel directly affiliated with this study and/or their immediate families. Immediate family is defined as a spouse, parent, child, or sibling, whether biological or legally adopted.
- 30. Are pregnant, or intend to become pregnant or to breastfeed during the study.
- 31. Are, in the judgment of the investigator, actively suicidal and therefore deemed to be at significant risk for suicide.

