9.3. Statistical Analyses

9.3.1. General Considerations

Statistical analysis of this study will be the responsibility of Lilly or its designee.

Any change to the data analysis methods described in the protocol will require an amendment only if it changes a principal feature of the protocol. Any other change to the data analysis methods described in the protocol, and the justification for making the change, will be described in the SAP or the clinical study report (CSR). Additional exploratory analyses of the data will be conducted as deemed appropriate.

Unless otherwise noted, all tests of treatment effects will be conducted at a 2-sided alpha level of 0.05, and confidence intervals will be calculated at 95%, 2-sided. All tests of interactions between treatment groups and other factors will be conducted at a 2-sided alpha level of 0.10.

Baseline is defined as the last non-missing measurement recorded on or before the randomization visit, prior to first dose of intervention, unless otherwise specified.

Primary estimand of interest and efficacy assessment

The primary estimand is a precise definition of the treatment effect to be estimated. The primary estimand of interest is comparing efficacy of LY3473329 doses to placebo and is named the "efficacy estimand" (Section 3). The efficacy estimand represents the efficacy prior to discontinuation of intervention. The primary efficacy assessment guided by the efficacy estimand will be conducted using the EAS (Section 9.2).

Secondary estimand of interest

The secondary estimand of interest is comparing efficacy of LY3473329 doses to placebo and is named the "treatment-regimen estimand" (Section 3). The treatment-regimen estimand represents the efficacy regardless of discontinuation of intervention. The secondary efficacy assessment guided by the treatment-regimen estimand will be conducted using the FAS (Section 9.2).

Safety assessments

Unless specified otherwise, safety assessments will be guided by an estimand comparing safety of LY3473329 doses with placebo irrespective of adherence to intervention. Thus, safety analyses will be conducted using the SS (Section 9.2).

Exploratory analyses

Additional exploratory analyses may be performed as deemed appropriate. Details will be provided in the SAP.

Continuous data

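### For baseline ALT/AST above 2.5x ULN, the Protocol 8.2.3 repeat-test trigger lies above the 7.1.1 limit of >5x ULN for more than 2 weeks, so no timed repeat serves that limit

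*Protocol*

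**What the plan says.** Four parts of the protocol bear on this point.

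- **Entry.** Section 5.2, criterion 27b, excludes only ALT or AST above 3.0x ULN. Baselines from above 2.5 to 3.0x ULN are therefore eligible, unless the investigator rejects them on judgement under criterion 26.
- **Close monitoring.** For a transaminase baseline below 1.5x ULN, Section 8.2.3 asks for the 48-72 h repeat from 3x ULN. For a baseline of 1.5x ULN or more, the trigger is "ALT or AST ≥2x baseline". If the abnormality persists or worsens, monitoring "should be done at a frequency of 1 to 3 times weekly" follows at first.
- **Stopping.** Section 7.1.1 interrupts or discontinues drug at "ALT or AST >5x ULN for more than 2 weeks". This limit has no baseline adjustment. The immediate limit is above 8x ULN.
- **Scheduled tests.** After dosing starts, the Schedule of Activities (1.3) has chemistry at Weeks 1, 2, 4, 8 and 12, at early discontinuation and at Visit 801. Visit 8 has none.

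Section 8.2.3 does not itself define baseline. Section 9.3.1 does: "Baseline is defined as the last non-missing measurement recorded on or before the randomization visit", before the first dose.

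**The concern.** An alert should fire before, or at, the limit it serves. Here, for a small group, it fires after. The order matters because this stopping limit includes a duration: one draw cannot establish it, and a second sample more than 14 days later is needed.

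A participant with a normal baseline who reaches 5.5x ULN must be re-tested in two to three days. That participant also meets the comprehensive-evaluation trigger, "or ALT or AST ≥5x ULN". A participant with a baseline of 2.8x ULN and the same value meets neither requirement. Unless the investigator acts on judgement, the next test is the next scheduled visit and dosing may continue until then. For a value first seen at Week 8, that visit falls at about the end of the 12-week dosing, so the limit could hardly shorten treatment.

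**Working it through.** The plan gives no figure to reproduce. The check compares thresholds and then visit intervals.

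**Thresholds.** Let B be the baseline in multiples of ULN, with B between 1.5 and 3.0 (8.2.3 and criterion 27b). The repeat trigger is 2B. The asymptomatic comprehensive-evaluation trigger at raised baseline is 3B. The stopping limit is fixed at 5. The uncovered band runs from 5 to 2B, with width max(0, 2B − 5).

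| B | Repeat trigger 2B | Comprehensive trigger 3B | Uncovered band (x ULN) |
|---|---|---|---|
| 1.5 | 3.0 | 4.5 | none |
| 2.0 | 4.0 | 6.0 | none |
| 2.5 | 5.0 | 7.5 | none |
| 2.6 | 5.2 | 7.8 | 5.0-5.2 |
| 2.8 | 5.6 | 8.4 | 5.0-5.6 |
| 3.0 | 6.0 | 9.0 | 5.0-6.0 |

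Example: 5.5 / 2.8 = 1.96, which is below 2. Neither the repeat nor the comprehensive evaluation is triggered.

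**Intervals.** The visit windows in 1.3 are ±2, ±3, ±3, ±4 and ±4 days for Weeks 1, 2, 4, 8 and 12. The wait to the next scheduled chemistry is the nominal gap ± the sum of the two windows.

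- Week 1 to 2: 7 ± 5 = 2-12 days
- Week 2 to 4: 14 ± 6 = 8-20 days
- Week 4 to 8: 28 ± 7 = 21-35 days
- Week 8 to 12: 28 ± 8 = 20-36 days

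From Week 4 or Week 8 the next scheduled test is always beyond day 14, by 20 − 14 = 6 to 36 − 14 = 22 days. Waits from Weeks 1 and 2 are shorter, and the point does not rest on them.

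**Numbers affected.** The documents do not say how many participants will have B above 2.5. If 0.5% to 2% is assumed, that is 0.005 × 233 = 1.2 to 0.02 × 233 = 4.7 participants. The active arms hold 5/7 × 233 = 166 participants, giving 0.8 to 3.3. Only those who also enter the band would be affected.

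**The case against.** The strongest reply has four parts.

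1. **The table can be read another way.** Its rows say ALT or AST, and any one row suffices. Read literally, a participant with ALT at 2.8x ULN but AST below 1.5x ULN at baseline also meets the first row, and the repeat is due at 3x ULN. This stands as a limit on scope. The gap exists on a per-enzyme reading, or when both transaminases were at least 1.5x ULN at baseline. Another liver test reaching its own trigger would also prompt the repeat.

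2. **Section 8.2.2 already asks for repeats.** It covers "All laboratory tests with values considered clinically significantly abnormal" and continues until they resolve. Its definition of clinical significance turns on whether the finding is associated with the underlying disease, so a new transaminase above 5x ULN would ordinarily qualify. Section 7.1 also allows discontinuation for "a clinically significant change in a laboratory value that, in the opinion of the investigator, merits discontinuation of study intervention". This largely stands: a repeat is likely. But both provisions depend on judgement and neither sets an interval.

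3. **The two-week limit itself implies a re-test.** An investigator who knows it would order one. That is reasonable, but 8.2.3 is where the protocol sets timed repeats, and it is silent here.

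4. **Baseline-relative triggers look deliberate.** They recur through 8.2.3, and as a general approach they are sound. Nothing in the text explains why the trigger should pass a fixed stopping limit.

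A reader might infer a wider fault: that the symptom-based limits, the ALP limits and the INR criterion are undermined too. The documents do not support that. The symptom and ALP limits can be applied from the draw itself, and the Appendix 10.6 tests to which 8.2.3 refers include PT-INR.

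**Conclusion.** The point holds, as a minor one. For baseline ALT or AST above 2.5 and up to 3.0x ULN, the required repeat starts above the stopping limit it should serve. What is missing is a timed trigger.

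A reader might go further and conclude that the limit cannot be applied, or that participants will be left on drug. Neither follows. A Week 4 value can still be judged, late, at Week 8, and 8.2.2 would usually prompt an earlier test. Baselines of 1.5 to 2.5x ULN are unaffected for this limit. With symptoms, bilirubin above 2x ULN or INR above 1.5, separate limits in 7.1.1 apply from 3x ULN without a waiting period.

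The size rests on three assumptions:

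- the table is read per enzyme, or both transaminases were raised at baseline;
- the last pre-dose value also respects the 3.0x ULN entry limit (at 3.5x ULN the band would be 5.0-7.0x ULN);
- the share with such baselines is an assumption and not a figure from the plan.

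Harm would further need an asymptomatic rise into a narrow band, first seen at Week 4 or Week 8, lasting more than two weeks, with no action by the investigator.

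**What to change.** In the raised-baseline ALT/AST row of the 8.2.3 close-monitoring table, require the 48-72 h repeat at *ALT or AST ≥2x baseline or >5x ULN, whichever is lower*, and state that the rows apply per enzyme. The two changes belong together: the per-enzyme statement alone would remove the cover that the literal reading gives.

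With the change, the trigger is capped at 5x ULN for baselines of 2.5 to 3.0x ULN. The uncovered band shrinks from at most 1.0x ULN to zero, and baselines of 2.5x ULN or less keep their present trigger of twice baseline. Persistent values then enter the 1-to-3-times-weekly monitoring, so the two-week limit can be judged on time.

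The cost is a wording amendment and a few extra blood draws. No change to the symptom, ALP or PT-INR provisions is needed for this point.

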Hepatocellular Drug-Induced Liver Injury Screening Plot (TBL vs. ALT or AST)	SS
Hepatocellular Drug-Induced Liver Injury Screening Table	SS
Cholestatic Drug-Induced Liver Injury Screening Plot (TBL vs. ALP)	SS
Cholestatic Drug-Induced Liver Injury Screening Table	SS
Participant profiles will be created for participants meeting criteria for a comprehensive hepatic evaluation (as defined in the protocol). Participant profiles will include demographics, disposition, information collected on the hepatic safety CRFs (where applicable) and a display of study drug exposure, adverse events, medications, blood pressure, heart rate, and the liver -related measurements over time.	SS

Abbreviations: ALP = alkaline phosphatase; ALT = alanine aminotransferase; AST = aspartate aminotransferase; CRF = case report form; DBL = direct bilirubin; INR = international normalized ratio, GGT = gamma-glutamyl transferase; TBL = total bilirubin; ULN = upper limit of normal. Planned and unplanned measurements will be included. The measurements do not need to be taken at the same blood draw. Maximum baseline will be the maximum non-missing observation in the baseline period. The maximum value will be the maximum non-missing value from the postbaseline period.

The primary purpose of the screening plots is to identify participants whose data warrant further review. For these plots, symbols will be used to indicate the randomized treatment.

For individual participants of interest, participant profiles will be reviewed. The review will include which treatment the participant was taking over time, the changes in hepatic labs over time, and the temporal association with potential causes. The review of participant profiles will also include the identification of any potential Hy's law case or potential cholestatic liver injury case that could have been missed by focusing only on the maximum values when determining 30-day time associations.

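### Section 7.1.1 gives participants with Gilbert's syndrome a direct-bilirubin stopping criterion, but Section 8.2.3 exempts them from every total-bilirubin trigger with no substitute, so meeting that criterion need not lead to a comprehensive liver evaluation

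*Protocol*

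**What the plan says.** Four places bear on this.

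- **Entry (Protocol 5.2, criterion 27c).** The exclusion reads "bilirubin > 1.5x ULN, except for participants diagnosed with Gilbert's syndrome". The protocol therefore knowingly enrols people with this diagnosis, including some with raised bilirubin.
- **Stopping (Protocol 7.1.1).** Two criteria use bilirubin: "ALT or AST >3x ULN and either TBL >2x ULN or INR >1.5" and "ALP >2.5x ULN and TBL > 2x ULN". Both carry the same exception: "In participants with Gilbert's syndrome, doubling of direct bilirubin should be used for drug interruption/ discontinuation decisions rather than TBL >2x ULN".
- **Monitoring and evaluation (Protocol 8.2.3).** The close-monitoring and comprehensive-evaluation tables each have two TBL rows, one per baseline TBL category. All four exempt Gilbert's syndrome. For baseline TBL at or above 1.5x ULN the entries are "TBL ≥1.5x baseline, except for participants with Gilbert's syndrome" for close monitoring and "TBL ≥2x baseline (except for participants with Gilbert's syndrome" for comprehensive evaluation. No row or sentence supplies another bilirubin marker for the exempted group, and none says that a met 7.1.1 criterion calls for the comprehensive evaluation.
- **SAP 4.6.7.1.1 (Table EKBC.4.5).** "Participant profiles will be created for participants meeting criteria for a comprehensive hepatic evaluation (as defined in the protocol"). Automatic profiles therefore depend on the 8.2.3 triggers, not on the 7.1.1 criteria.

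**The concern.** Section 7.1.1 recognises that total bilirubin is a poor signal in Gilbert's syndrome and replaces it. Section 8.2.3 removes it and puts nothing in its place. The two sections then disagree about the same participant: one says the liver picture is serious enough to interrupt or discontinue drug, and the other does not ask for the work-up that looks for a cause.

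Two things are at stake. First, under 7.1.1 resumption depends on finding a self-limited, non-drug cause, yet the tests most likely to find one (INR, viral and autoimmune tests, imaging) are not required for this participant. Second, a transaminase-plus-bilirubin case in this group would not automatically produce a participant profile in the study report, while the parallel case in another participant would.

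**Working it through.** The plan gives no figure to reproduce. The check applies the thresholds of 7.1.1 and 8.2.3 to the same laboratory picture with and without Gilbert's syndrome. All limits are multiples of ULN. INR is normal and there are no hepatic signs or symptoms. Doubled direct bilirubin is taken as met.

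**Inputs, for baseline ALT/AST, ALP and TBL all below 1.5x ULN**

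| Rule | Without Gilbert's | With Gilbert's |
|---|---|---|
| 7.1.1 stop, ALT/AST route | ALT/AST >3x and TBL >2x | ALT/AST >3x and direct bilirubin doubled |
| 7.1.1 stop, ALP route | ALP >2.5x and TBL >2x | ALP >2.5x and direct bilirubin doubled |
| 8.2.3 comprehensive, ALT/AST | ≥5x | ≥5x |
| 8.2.3 comprehensive, ALP | ≥3x | ≥3x |
| 8.2.3 comprehensive, TBL | ≥2x | none |
| 8.2.3 close monitoring | ALT/AST ≥3x, ALP ≥2x or TBL ≥2x | ALT/AST ≥3x or ALP ≥2x |

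**Step 1, ALT/AST route.** For a Gilbert participant the stopping criterion is met above 3x and comprehensive evaluation starts at 5x. The gap is 3 < ALT/AST < 5. At ALT 4x: 4 > 3, so the stopping criterion is met; 4 < 5 and the TBL row is exempt, so no comprehensive row applies.

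**Step 2, same criterion without Gilbert's.** Here TBL >2x is needed to stop, and TBL >2x always satisfies TBL ≥2x. There is no gap.

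**Step 3, ALP route.** For a Gilbert participant the gap is 2.5 < ALP < 3. Without Gilbert's it closes as in Step 2.

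**Step 4, higher baseline enzymes.** Criterion 27b excludes only "alanine aminotransferase (ALT) or aspartate aminotransferase (AST) >3.0x upper limit of normal (ULN"), so baseline ALT/AST (b) can be as high as 3x at screening. For b ≥1.5x, comprehensive evaluation without symptoms starts at 3 × b and close monitoring at 2 × b.

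- b = 2x: comprehensive at 3 × 2 = 6x, so the gap is >3x to <6x. Close monitoring starts at 2 × 2 = 4x, so >3x to <4x meets the stopping criterion but neither table.
- b = 3x: comprehensive at 3 × 3 = 9x, so the gap is >3x to <9x. Close monitoring starts at 2 × 3 = 6x.
- Baseline ALP 2x: both tables start at 2 × 2 = 4x, so >2.5x to <4x meets neither.

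With baseline TBL below 1.5x ULN, a participant without Gilbert's is still caught by the TBL rows in all these cases.

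**Step 5, what remains in the ALT 4x example.** Close monitoring applies (4 ≥ 3). For the hepatic CRF, condition 1 needs ALT ≥5x on consecutive tests, condition 2 exempts Gilbert's at this baseline TBL, and condition 3 concerns ALP. That leaves an SAE or discontinuation for a hepatic event. In the ALP gap, condition 3 (≥2x ULN on consecutive tests) would bring in the CRF if the value is confirmed.

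**Step 6, CRF condition 2.** Its main line exempts known Gilbert's syndrome when baseline TBL is below 1.5x ULN. Its sub-line, for baseline TBL at or above 1.5x ULN, does not repeat the exemption. Read literally, a Gilbert participant going from 1.5x to 3x ULN (3 / 1.5 = 2) triggers the CRF, while one going from 1.4x to 3x ULN does not.

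**The case against.** The best defence is that such a participant is far from unattended, and most of it stands.

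- **Close monitoring is more than a repeat test.** In the ALT 4x example, tests including direct bilirubin are repeated within 48 to 72 hours. If the abnormality persists, the investigator evaluates possible causes with the medical monitor, including examination and full history, and tests 1 to 3 times weekly at first.
- **Section 7.1.1 is itself a safeguard.** Drug is interrupted or discontinued, and resumption needs medical-monitor consultation and an identified non-drug cause. Discontinuation for a hepatic event brings in the hepatic CRF, and permanent discontinuation due to an adverse event brings in a narrative (SAP 4.6.3).
- **The SAP does not hide the case.** The screening plots and tables use the safety set with no Gilbert exclusion. Profiles of participants of interest are reviewed, and direct bilirubin is tabulated against multiples of ULN.

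None of this requires the comprehensive work-up or creates the profile automatically.

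A reader might go further in four ways that the documents do not support.

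- That these participants never get a comprehensive evaluation. With baselines below 1.5x ULN they do at ALT/AST ≥5x, at ALP ≥3x, or at ALT/AST ≥3x with signs or symptoms.
- That the entry exception in 27c causes the gap. It explains why the group is present, but the gap arises at any baseline TBL. The clean contrast with other participants in fact needs baseline TBL below 1.5x ULN. At baseline 1.6x, a TBL of 3x is 3 / 1.6 = 1.9 times baseline, so a participant without Gilbert's would also miss the row set at twice baseline.
- That the hepatic CRF is always missed. Step 6 shows otherwise for baseline TBL at or above 1.5x ULN.
- That ignoring an isolated rise in direct bilirubin is specific to Gilbert's syndrome. No 8.2.3 row uses direct bilirubin as a trigger for anyone.

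**Conclusion.** The inconsistency is real and limited. For a Gilbert participant without hepatic signs or symptoms, and with baselines below 1.5x ULN, a bilirubin-linked stopping criterion can be met with no comprehensive-evaluation row met. This happens at ALT/AST >3x to <5x ULN or ALP >2.5x to <3x ULN. The range widens with higher baseline enzymes, where part of it also misses close monitoring. What is lost is the mandatory wider work-up and the automatic SAP profile. CRF condition 2 is separately inconsistent on the exemption.

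The size is stated as laboratory ranges because the documents give no prevalence of Gilbert's syndrome. A prevalence would in any case count exempted participants, not those who reach the gap within 12 weeks. The number is probably small. The case for correction rests on the seriousness of the pattern and the low cost of the change, not on an expected count.

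**What to change.** **Protocol.** Sections 7.1.1 and 8.2.3 must be reconciled for participants with Gilbert's syndrome. This covers the TBL rows of both the close-monitoring and comprehensive-evaluation tables, and condition 2 for the hepatic CRF. The sponsor's clinical team decides the marker and the limits; this review proposes neither.

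**SAP 4.6.7.1.1.** Flag Gilbert participants in the hepatocellular and cholestatic screening plots and tables. Extend the profile rule to any participant who meets a Section 7.1.1 stopping criterion, including in its Gilbert form.

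**Cost.** Wording in the protocol sections named, and a small amount of extra programming for the SAP. Direct bilirubin is already in the chemistry panel (Protocol Appendix 2) and drawn at Visits 1 to 7, early discontinuation and Visit 801. Pre-existing conditions are recorded at Visit 1. No new sample is needed.
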